The ePartogram intervention includes features to benefit SBAs, as well as supervisors and health officials:

SBAs:

- Automated plotting of clinical data
- Reminders for when to take measurements (beeps)
- Alarms for abnormal clinical measurements (red colored tabs or cells)
- Facilitates recording of medications administered and notes on client condition
- Data sharing between tablets actively used by SBAs for coordinated care on laboring woman
- Referral form and data sharing between facilities
- Ability to print paper record to remain at the facility

Supervisors and Health Officials:

- Supervisor function allows for viewing partograph data in real-time, facilitating supervision and communication on care
- Completed client records available for review and audits
- Online database with monthly reports and raw data for analysis
- Online dashboard with monthly summary reports and visual representations of key data

Prior ePartogram Study

¹ A reminder is an auditory and visual alert automatically triggered within the ePartogram. The reminder indicates when a specific measurement should be taken and recorded in the ePartogram.

² An alarm is a visual alert automatically triggered within the ePartogram to indicate when a clinical measurement is outside of the normal range, as defined by WHO guidelines and augmented by Jhpiego clinicians. Alarms can be “low-level” which is indicated as pink in the ePartogram and alerts providers to pay attention to the clinical measurement or “high-level” which is indicated in red in the application and alerts providers that clinical action may be needed. (see Appendix B for more detail)

³ “Clinical rules” refers to a document the defines the reminders and alarms “low-level” and “high-level” that are programmed into the ePartogram

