 - a. The training will be on routine labor monitoring and using the partograph as a decision-making tool. Facilities will receive stocks of any supplies and drugs that are needed for monitoring or normal labor and management of complications and referrals.
 - b. This training will cover how to fill out the Ministry of Health register on each woman/newborn.
 - c. ePartogram sites will also receive two days of training on using the Android-based ePartogram tablet 'app', maintaining the tablet computer, and standard operating procedures for tablet use and storage to

ensure data confidentiality. SBAs passing the ePartogram post-training test will be asked use the ePartogram during clinical care.

- 5) In both ePartogram and paper-partograph sites, **facility readiness** will be ensured. Enough copies of standard-of-care paper partographs will be available on site at facilities in both study groups, and supplies/equipment (i.e. blood pressure apparatus).
- 6) In **ePartogram** facilities:
 - a. Software support procedures if needed will be set up.
 - b. Standard Operating Procedures (SOPs) will be created for ownership of tablets, maintenance, and what to do in case of tablet malfunction or loss and Jhpiego's ongoing support.
 - c. Data coordinator will be on call to troubleshoot eP software questions
- 7) In **ePartogram** facilities, each participating provider will use the ePartogram tablet and application on women in labor.
 - a.) At ePartogram sites, all data entered into the ePartogram will automatically sync to the server when connected to the internet and saved to a secure, cloud-based, password-protected website. The partograph and outcome data will be accessed at least two times per week by the study coordinator.
 - b.) A designated onsite records-management staff or, in the absence of such staff, the nurse in-charge will take photographs of the Ministry of Health **register book**, weekly--where aspects of the care to a woman/newborn(s) are written in one row. This has info on the health outcomes.
 - c.) If paper partographs are used at ePartogram sites, this data will still be included in the ePartogram group.
- 8) In the **control sites**, the paper partograph will be used for labor monitoring/management. Providers will have available paper partographs, which is the standard of care for use during service delivery.

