- *Outcome indicator*: The value for the outcome, ‘appropriate clinical actions for complications’, is unknown and thus 50% gives the most conservative estimate for the facilities in the control group using the paper partographs.
- *Effect size*: We expect a 30% point improvement on this indicator in facilities using ePartogram, the intervention sites, to 80%.

Adjusted for design effect, the total number of partographs or ePartograms needed are 1004 per study group, or 2009 in both groups. Due to the fact that there may be additional changes to facility selection, this number of partographs to review may increase somewhat based on the formulas. So we request the number of partographs to review to be up to **2,200 in total** .

Table 1. Sample Size Calculation Parameters

Table 1. Sample size scenarios for ePartogram effectiveness study

Availability of partographs in selected sites per month	536.8	Proportion of all births that have a partograph filled out	80%	671	1342	All 12 facilities - births monthly
Cluster size (Average) (formula based on 3 cells)	17.0					
Intra-class correlation coefficient (ICC)	0.15					
Number of clusters (facilities) PER ARM	6	(total 12 facilities in both study arms)				
Proportion of women whose labor crosses the Action line (a)	19%		Design effect (formula based on cells)	5.3		
Coefficient of variation (determined from number)	90%					
Effective Size: Detecting difference between arms on main indicator: "Case is appropriately managed"	Comparison group	ePartogram group	Unadjusted sample size (in a simple random sample) to detect difference	Adjusted for design effect	Total no of partographs required per arm	Total no of partographs or ePartograms: both study arms
	50%	70%	90	482	2536	5071
	50%	75%	55	293	1543	3087
	50%	80%	36	191	1004	2009

Sample size for qualitative interviewing

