1	Health Worker Line Listing	Study team will use this to assign a unique provider id to skilled birth attendants working in each facility who consented to the study and were trained by study staff. This provider study id will then be written on paper partographs, in ePartograms and on registers, when names are obscured (to account for clustering of data in the provider). We will record cadre, years of experience, and date passed labor management and ePartogram competency test.
2	Partograph or ePartogram file on each laboring woman (a)	The top portion of the partogram is completed on admission with information about: woman's name, gravida, parity, hospital id number, date and time of admission, and whether membranes are ruptured. At regular intervals, the following measurements are obtained by the provider: fetal heart rate, condition of amniotic fluid, moulding, descent of head, cervical dilation, contractions, oxytocin, drugs and IV fluids given, pulse, blood pressure, temperature, urine protein, acetone and volume.
3	Stamp on the paper partograph or programmed into the app (for ePartogram).	In this study, the paper partograph and ePartogram will include additional fields related to maintaining normal labor and management of abnormal conditions. The stamp will be placed on the paper partograph or programmed into the app (for ePartogram). Standard provider actions will be recorded (e.g. ambulation, nutrition, fluid intake, presence of a birth companion, oxygen administration, changing the mother's position for choice or due to fetal heart rate, presence of bleeding). Providers will also indicate if a consultation with another provider was made for the client and if the client was transferred (reason for referral), fresh stillbirth, or early newborn death.

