4	Partograph Extraction tool (revised July 2017)	There are sections where the data extractors will enter the information on the woman and newborn conditions and outcomes that appears a) at the top of the partograph, b) at the bottom of the partograph and c) provider actions recorded on the Jhpiego stamp tool. There are repeatable sections that also allow for data entry on the actual values of the measurements are recorded for 13 parameters (fetal heart rate, cervical dilation, systolic and diastolic blood pressure, amniotic fluid, moulding, head descent, contractions, pulse, temperature, urine protein, acetone and volume). These data will be recorded for each 30 minute interval for the duration of the active stage of labor (4cm dilation to 10cm dilation).
5	Register review tool	This tool will contain the abstracter id, date and facility id, month number of deliveries, Live births (spontaneous, assisted, cesarean, breech), fresh stillbirths, macerated stillbirths, number of twins, early neonatal deaths, number referred, number of maternal deaths
6	Qualitative discussion field guide for ePartogram sites (in-depth interviews or small focus groups)	Qualitative interviews will be conducted with providers in each study arm. In the ePartogram group, qualitative interviews will be administered to better understand the benefits and challenges of ePartogram. Providers will be asked about their experience in using the ePartogram, opinions on various features of the application, and implementation considerations for ePartogram.
7	Qualitative discussion field guide for paper partograph sites (in-depth interviews or small focus groups)	Qualitative interviews will be conducted with providers in the paper partograph group to better understand how providers use the paper partograph in a variety of labor and delivery settings, perceived benefits and challenges in using paper partograph, and the facility conditions that enable or hinder adoption of best practices in labor management

(a) Existing tool already in use

2. Describe the **number and type of study visits and/or contacts** between the study team and the participant, how long they will last, and where/how they will take place.

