P2. Decision-making and actions taken to maintain normal labor (Tool 4)	Data on each partograph parameter will be entered for each time period, as well as actions taken in labor. Jhpiego clinical rules will be applied to the data in the extraction database to determine appropriate clinical actions for a labor without any complication. This is a binary variable.	Labors in which Section 3 marked as “Normal Labor”	First, we will examine the frequency/prevalence of each clinical action taken in normal labor and compare between the two study groups. Second, we will carry out same analysis as for Objective P1.
P3. Detection, decision-making and action to address deviations from normal labor and complications arising during labor—for ‘slow’ labor, prolonged labor, obstructed labor and cephalo-pelvic disproportion	Data on each partograph parameter will be entered for each time period, as well as actions taken in labor. Jhpiego clinical rules will be applied to the data in the extraction database to determine appropriate clinical actions for a labor with a specific complication. This is a binary variable.	Labors in which Section 3 marked “Slow labor, prolonged labor, obstructed labor or cephalo-pelvic disproportion”	First, we will examine the frequency/prevalence of each clinical action taken in selected complications and compare between the two study groups. Second, we will carry out same analysis as for Objective P1.
-- for all complications (Tool 4)	Same as above. A composite variable will be created for all complications. This is a binary variable.	Labors in which Section 3 marked as ANY complication	First, we will examine the frequency/prevalence of each clinical action taken in all

			complications and compare between the two study groups. Second, we will carry out same analysis as for Objective P1.
S1. Is facility use of ePartogram (vs. paper-partograph) associated with lower rate of...?			
From the Register Analysis			
Neonatal deaths <24 hours and (Tool 5)	Number of early neonatal deaths. This is a count variable.	All live births	We will compare means using t-tests across 2 groups. Next, we will use unadjusted regression models that account for clustering (correlation) of data within the facility. Poisson regression with offset term (or another appropriate model to be explored) will be used for bivariate and multivariable analysis.

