ePartogram will enter the provider's study id number. There will be a drop-down menu in which the provider name and study id appears, but only provider study id will end up in the back-end database. There will be no names kept in the database of ePartogram information.

Each time the study staff visits the facility, the health worker line listing forms and database will be updated with names of new providers added to the study and for intervention sites only, who pass the post-training test for ePartogram

Written consent forms will be kept for 3 years after the study date of closing with IRB.

- a. *register review analysis:* The register has a field for provider name. Prior to our taking scan/photo of registers, we will obscure the provider name and replace the provider name with the provider study id from the Health Worker Line Listing.

Identifiers of Women

- a. *partograph review analysis:* The name of the client/woman is on the partograph. Prior to photographing partographs, we will make sure the partograph has the woman's 'hospital admission number'. We will verify that this is the same as recorded in the register. Once the admission number is verified, then we will scan/photocopy the partograph and obscure the woman's name by covering with a small piece of paper prior to scanning the partograph.
- b. When a new client sheet is started in the ePartogram, the software will automatically assign a study-generated ID number to each laboring woman's eParotgram record. This record will also have the woman's name during the care process, for printing the ePartogram record to leave at the facility. The study ID will be the facility number (i.e. MER01 for the first facility in Meru) + date + 01 for the first woman admitted in labor.
- c. *register review analysis:* The register has a field for woman's name. When we scan/photocopy the register, we can obscure women's names.

Identifiers of Providers - for Qualitative Interviews.

We may temporarily keep track of provider and supervisors names only for the purpose of setting up an interview at a convenient time. However, no names or identifiers will be collected or recorded on qualitative participants.

The names of providers receiving any payment or reimbursement as described in the consent form will be retained for financial purposes only in secure financial database at Jhpiego.

6. Answer the following if they are relevant to your study design:

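### P2 and P3 count only actions the provider recorded, and the ePartogram makes recording easier, so part of a difference between arms may be better documentation rather than better care

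*Combined protocol and SAP*

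**What the plan says.** Section I asks three primary questions. P1 covers monitoring and its recording on the partograph. P2 and P3 ask about decisions made and actions taken. Table 5 (V.C.4) scores P3 by clinical rules "applied to the data in the extraction database to determine appropriate clinical actions for a labor with a specific complication", with the same approach for P2. All three use Tool 4, the extraction tool.

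Table 4 shows where the action data come from. Tool 4 takes them from the chart and the stamp. Tool 3 is that stamp, placed on paper or programmed into the app: "Standard provider actions will be recorded" there by the provider. Section II lists among the ePartogram's features for birth attendants: "Facilitates recording of medications administered and notes on client condition". It also names awkward data entry and the lack of real-time data collection as weaknesses of paper that the app addresses.

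A second record exists in both arms. The register is photographed weekly (III.A, items 7b and 8b) and is described as a book "where aspects of the care to a woman/newborn(s) are written in one row". Tool 5 abstracts from it, as counts, "Live births (spontaneous, assisted, cesarean, breech") as well as referrals.

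Section III.B sizes the trial on P3. The control rate is unknown, "thus 50% gives the most conservative estimate for the facilities in the control group using the paper partographs", and the plan states: "We expect a 30% point improvement on this indicator in facilities using ePartogram, the intervention sites, to 80" per cent.

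**The concern.** Exposure to the ePartogram may change care, and it may also change how completely care is written down. P2 and P3 cannot separate the two, because the numerator has one source and that source is part of the intervention. Adjustment for facility, provider and woman-level confounders does not remove measurement error that differs by arm.

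The only source check described for these data (III.A, item 9c) compares the register with the medical record. It does not test whether an action missing from a partograph was done, or whether a recorded one was not.

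The stake is interpretation. The Ministry is to be informed about effectiveness, and P1 already covers recording. If P2 and P3 are reported as actions taken, a gain in documentation could be read as a gain in labor management.

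**Working it through.** **Plan's own figure.** Inputs from III.B and Table 1: 50% versus 80%, ICC 0.15, cluster size 17.0, coefficient of variation 0.90, 19% of labors eligible. Alpha and power are not stated; two-sided 0.05 and 80% are inferred because they reproduce the table.
- Unadjusted n = (1.960 + 0.842)² × (0.50×0.50 + 0.80×0.20) / 0.30² = 35.8 per arm (plan: 36).
- Design effect = 1 + (17.0 − 1) × (1 + 0.90²) × 0.15 = 5.34 (plan: 5.3).
- 35.8 × 5.34 = 191 complicated labors; 191.1 / 0.19 = about 1,006 partographs per arm (plan: 1,004).

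The plan's figure reproduces. The design carries the information of about 35.8 independent cases per arm.

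**Recording model.** Let q be the true rate of appropriate action, the same in both arms, and r the chance that the actions needed for the score are recorded when done (r0 paper, r1 app). With no false entries, the observed rate is q × r and the spurious gap is q × (r1 − r0).

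All three quantities are assumptions. Section II offers two proxies from an earlier Kenyan survey: appropriate action in 78% of cases reaching the action line, and all chart components completed in 58% of cases. Neither is a recording rate for actions.

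| q | r0 | r1 | Observed P3 | Gap (points) | Chance of p < 0.05 |
|---|---|---|---|---|---|
| 0.78 | 0.80 | 0.90 | 62.4% v 70.2% | 7.8 | 11% |
| 0.78 | 0.70 | 0.90 | 54.6% v 70.2% | 15.6 | 28% |
| 0.78 | 0.58 | 0.80 | 45.2% v 62.4% | 17.2 | 32% |
| 0.78 | 0.58 | 0.90 | 45.2% v 70.2% | 25.0 | 60% |
| 0.78 | 0.58 | 0.95 | 45.2% v 74.1% | 28.9 | 74% |

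The last column applies a normal-approximation two-proportion test to 35.8 effective cases per arm; the nominal level is 5%. At q = 0.80 the first and last gaps become 0.80 × 0.10 = 8.0 and 0.80 × 0.37 = 29.6 points.

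**What 30 points would need.**
- At q = 0.78 and r0 = 0.58, r1 must be at least 0.58 + 0.30/0.78 = 96.5%.
- An exact 50% versus 80% needs q × r1 = 0.80 with r1 ≤ 1, so q ≥ 80% and r0 = 0.50/q ≤ 62.5%.
- If q = 78% and control reads 50%, recording alone can add at most 28 points; if q = 70%, at most 20.

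**Paper use at ePartogram sites.** Such labors stay in the ePartogram group (III.A item 7c; V.C.6f). If a share s of them is on paper and recorded at r0, the gap shrinks by the factor 1 − s. The 28.9-point case becomes 28.9 × 0.9 = 26.0 at an assumed 10%, and 28.9 × 0.8 = 23.1 at 20%.

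**Linkage.** Section V.C.5, item a under identifiers of women, says of the admission number: "We will verify that this is the same as recorded in the register". That item concerns charts about to be scanned, which means paper. Item b gives ePartogram records a software-generated study ID and describes no such check. Tool 2 lists a hospital number for both forms, so linkage looks feasible, but it is not written down for the ePartogram arm.

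**The case against.** The case on the other side has weight. The stamp puts the same added action fields on both forms. Both arms receive the labor-management training. Completeness is reviewed after the first 20 records per site and periodically after that. The feature quoted from Section II concerns medications and notes, not every stamp field. Section I openly labels P1 to P3 as partograph review, and the S1 deaths and stillbirths come from the register. These points should narrow the recording gap. They do not equalise reminders or ease of entry, and none verifies an action case by case.

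The model is also one-sided. Recording affects which labors enter the P3 set, which could bias the comparison in either direction.

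A reader might infer that better paperwork alone would deliver the whole planned effect. The documents do not support that: it needs the upper-end values shown above, and no recording rate for actions is given. Nor does the 30-point figure apply to P2, which has no stated effect size.

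A reader might also want the register to act as a test that P3 must pass. That does not stand. The register is kept by unblinded facility staff, shows few of the actions, and does not show whether an action was appropriate. Section II expects partograph use to reduce unnecessary operative interventions, so a real benefit could lower the very events the register shows.

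**Conclusion.** The concern holds in a limited form. P2 and P3 measure documented actions, and the arms may differ in documentation because of the intervention itself. Under the assumed values the spurious P3 difference is about 8 to 29 points with no change in care, and the chance of a significant result is 11% to 74%. These figures rest on assumed recording rates, on 78% true action in both arms, on no false entries, and on the plan's own design effect. They show what the design cannot exclude; they do not predict what will happen.

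Part of Section X (Study Management) was not available, so a check of recorded actions described there cannot be ruled out.

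**What to change.** 1. In Table 5 and in the conclusions, word P2 and P3 as documented actions.
2. For labors in the P3 set, enter the linked register row and co-report by arm the actions the register shows (cesarean, assisted delivery, referral) beside the same actions as recorded on the chart. Include chart-register agreement by arm. Treat this as a sensitivity analysis, not a pass/fail rule.
3. State that the ePartogram extract keeps the hospital or admission number listed under Tool 2, and that it is checked against the register as for paper charts.
4. Report P3 over a stated range of recording rates, dividing each arm's observed proportion by its assumed rate. For example, an observed 50% versus 80% with rates of 70% and 90% becomes 71.4% versus 88.9%, a difference of 17.5 points.

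The cost is wording plus row-level entry for about 0.19 × 2,009 = 382 labors (418 at the 2,200 ceiling), by the existing data clerks from photographs already taken. That the rows carry mode of delivery and referral is inferred from the Tool 5 counts and should be confirmed first. The downside is partial coverage: the register is another facility record, holds only some P3 actions, and says nothing about appropriateness.

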JHSPH IRB Research Plan for New Data Collection

PI Name: [name], Medical Director and Vice President, Innovations Jhpiego/Baltimore

Co-Investigators: [name], [name], [name], [name], [name], [name]

Study Title: ePartogram Effectiveness Study in Kenya

IRB No.: 6958

PI Version No./Date: July 14, 2017, v4

I. Aims of the Study: Describe the aims/objectives of the research and/or the project's research questions or hypotheses.

The study aim is to measure the effectiveness of use of the electronic partogram vs. the standard-of-care paper partograph on labor management outcomes and labor outcomes in maternity wards in Kenya.

Research Questions

Primary

Comparing facilities in which birth attendant/providers are using the ePartogram and facilities in which providers are using the paper partograph, are the following improved?: [\(partograph review\)](#)

- P1) compliance with globally-recommended, labor monitoring practices and recording on the partograph of the practices performed
- P2) decision-making and actions taken to maintain normal labor
- P3) detection, decision-making and action to address deviations from normal labor and complications arising during labor

Complications of interest are: prolonged labor (labors over 12 hours or labor that crosses the action line, may not be over 12 hours), arrest of descent/dilation that precedes obstructed labor; obstructed labor including arrest of descent/dilation, fetal distress and maternal distress; maternal infection; severe pre-eclampsia or eclampsia; fetal distress; and maternal distress with shock-like symptoms.

Secondary

In intervention and control sites:

S1) Is facility use of ePartogram (vs. paper-partograph) associated with **lower rate of** (neonatal death <24 hours and intrapartum death (fresh stillbirth rate)? [\(register review\)](#)

S2) What **facility conditions** and practices enable or hinder implementation of best practices in labor monitoring and decision-making? What makes the partograph/ePartogram easy-to-use? Efficient? [\(qualitative inquiry, facility assessment\)](#)

S3) What is the availability, accessibility, acceptability, and quality of **supervision/support** provided with eSupervision connectivity and referral functions of the partogram? [\(qualitative inquiry\)](#)

This study will inform the Ministry of Health on the effectiveness of the ePartogram and whether to use it more widely in Kenya.

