Intrapartum death (fresh stillbirth rate) (Tool 5)	Number of fresh stillbirths. This is a count variable.	All live births	Same as above.
Adverse perinatal events (Neonatal deaths <24 hours+ intrapartum death (fresh stillbirth rate))	Number of neonatal deaths and fresh stillbirths	All live births	Same as above.

Statistical analysis plan

Outcomes will be dichotomous, yes/no for each measure.

In the main statistical analysis of our primary outcomes, we will focus on program effect (intervention (ePartogram) group of facilities versus comparison (paper program) group of facilities) as the main predictor of interest. The analysis will be performed at the level of the individual case (partogram). In preliminary analyses we will conduct univariable and bivariable analyses to assess the distribution of key variables and joint distributions and unadjusted relationships.

In final analyses addressing study aims, we will fit multi-level, multivariable regressions models for the outcomes with adjustment for possible confounders and account for clustering by provider and/or study clinic by the use of GEE.

While we have selected clinics roughly matched between the intervention and comparison regions, we will still evaluate confounding to attain the least biased estimate of our intervention effect. Facility level possible confounders are: monthly case load of laboring women, number of providers, key equipment availability etc. Provider-level possible confounders that may be adjusted for are years of work experience since graduation and cadre. Woman-level possible confounders are age and parity.

5. Describe whether you are collecting or storing **personal identifiers**, and if yes, why you need them, and when and how you plan to dispose of them. Signatures on consent forms are considered to be identifiers.

Identifiers of Providers

Our study will assign each facility and each provider a study id number of the Health Worker Line Listing form to be updated monthly. This will be kept separately from partograph data.

partograph review analysis: the paper partograph has a place for a provider to sign it. When we scan/photocopy paper partographs, we will obscure the provider name (cover with lose paper) but will we add/write on it the provider study id number.

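### S1 asks about neonatal death within 24 hours, but the variables and register tool carry no 24-hour limit; the fresh stillbirth and composite rows also use a case set that excludes stillbirths

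*Combined protocol and SAP*

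**What the plan says.** Secondary question S1 in Section I asks whether the ePartogram lowers the rate of "neonatal death <24 hours and intrapartum death", the latter identified with the fresh stillbirth rate.

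Table 5 (Section V.C.4) turns this into three register outcomes:

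- The neonatal row is labelled "Neonatal deaths <24 hours and (Tool 5", so the label keeps the limit. The outcome cell beside it reads "Number of early neonatal deaths. This is a count variable".
- The fresh stillbirth row has the outcome "Number of fresh stillbirths. This is a count variable".
- The composite row again carries the 24-hour limit in its label, but its outcome cell reads "Number of neonatal deaths and fresh stillbirths".

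In all three rows the entry under cases is "All live births". The neonatal row plans a comparison of means and then a Poisson model with an offset. The offset variable is not named. The other two rows refer back to that analysis.

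The source is Tool 5, the register review tool. Table 4 describes it as facility counts by month, including live births by mode of delivery and "fresh stillbirths, macerated stillbirths, number of twins, early neonatal deaths". No age or time of death is listed.

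**The concern.** Table 5 names one outcome in the label and a different one in the variable. The analyst works from the variable and from what Tool 5 supplies, and neither carries the 24-hour limit. An S1 result could then be reported as death within 24 hours when the count behind it was never restricted in that way. S1 concerns deaths soon after birth, alongside intrapartum death. If the ePartogram acts mainly on those, adding later deaths pulls the estimate towards no effect. Without a written rule, facilities or abstractors may also count differently.

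The stillbirth rows have a second problem. Read as a case set, live births contain none of the events to be counted. Read as the Poisson exposure, the denominator depends on the outcome, because each stillbirth averted adds a live birth.

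**Working it through.** The plan gives no event rate, expected count or power for S1, so there is no S1 figure to reproduce. Its sample size calculation (Section III.B) serves P3 and is not affected.

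**Step 1. Can the limit be applied?** The limit appears in the S1 question and in the neonatal and composite row labels. It is absent from both outcome cells and from the Tool 5 field list. Those two outcome cells also differ from each other: one says early neonatal, the other only neonatal. No section defines either term. A monthly count without age or time of death cannot be split at 24 hours afterwards, so Tool 5 as described cannot deliver the labelled outcome unless abstractors apply a rule that the documents do not contain.

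**Step 2. Size if later deaths are counted.** Let s be the share of recorded deaths in the control arm that occur within 24 hours. The documents give no value; 50% to 90% is assumed.

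- The count exceeds the outcome asked for by a factor 1/s: 1/0.9 = 1.11 to 1/0.5 = 2.0.
- If only deaths within 24 hours respond, with risk ratio RR, and later deaths do not, the ratio on all recorded deaths is s × RR + (1 − s). With an illustrative RR of 0.70:
  - s = 0.9: 0.63 + 0.10 = 0.73
  - s = 0.7: 0.49 + 0.30 = 0.79
  - s = 0.5: 0.35 + 0.50 = 0.85

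**Step 3. Size of the denominator error.** Let r be the fresh stillbirth risk among live births plus fresh stillbirths. Dividing by live births gives r/(1 − r). The documents give no stillbirth rate, so the risks below are assumed.

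- Rates: 10 per 1,000 becomes 10.1, 20 becomes 20.4, 30 becomes 30.9, and 50 becomes 52.6.
- Ratio: the true RR is multiplied by (1 − r0)/(1 − RR × r0), where r0 is the control risk. At r0 = 0.05 and RR = 0.80: 0.80 × 0.95/0.96 = 0.792, a shift of 1.0%. At r0 = 0.05 and RR = 0.50: 0.50 × 0.95/0.975 = 0.487, a shift of 2.6%. The shift is away from no effect.
- If total births are preferred as the denominator, an assumed 10 macerated stillbirths per 1,000 in both arms leaves the largest shift at 2.6%.
- For the composite, both arms' rates are rescaled in the same way by 1/(1 − r), with r still the fresh stillbirth risk, so the same bound applies.

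**Step 4. Comparison with random error.** Section III.B gives 671 births per month in six facilities, and Section V.C.3 expects 2 or 3 months of collection: 1,342 to 2,013 births per arm. At an assumed 10 to 30 per 1,000, that is about 13 to 60 fresh stillbirths per arm. Even ignoring clustering, the standard error of the log rate ratio with equal counts is √(2/60) = 0.18 at best and √(2/13) = 0.39 at worst. One standard error is thus about 20% or more on the ratio scale, against a shift of at most 2.6%.

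**The case against.** The strongest reply is that the limit is in Table 5 after all. Both relevant row labels state it, as does S1. On this reading the label defines the outcome and the cell beside it is shorthand. The documents use similarly loose wording elsewhere: the partograph stamp (Table 4, Tool 3) and the adverse event monitoring (Section X.D) also refer to early newborn deaths without an age. The description of Tool 5 is one line, and the tool itself and its instructions are not shown. This part stands: it cannot be said that later deaths will be counted, only that nothing in the documents prevents it. It does not remove the defect, because a row label gives an abstractor no rule and a monthly total no means of checking one.

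A reader might go further and infer a bias against the ePartogram, since Section III.A fixes two named hospitals, one of them a teaching and referral hospital, as intervention sites, and sick newborns may stay longer in such places. The documents do not support this. They give no length of stay, do not say whether deaths after transfer to a newborn unit reach the maternity register, and intend the two groups to be similar in birth volume, staffing and level of obstetric care as far as possible. The dilution in Step 2 does not depend on that inference.

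On the denominator, the objection that the effect is negligible is correct. The live-birth entry stands in the cases column, and its use as the offset is the natural reading, not a stated one. The definition is still wrong as written.

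**Conclusion.** Both mismatches are confirmed by the text, with unequal consequences. The 24-hour mismatch matters more. As specified, S1 would report an outcome that its variables and source tool do not measure. If later deaths enter, an effect confined to the first 24 hours shrinks, for illustration from 0.70 to between 0.73 and 0.85. That range rests on an assumed ratio, on assumed shares of 90% to 50%, and on no effect on later deaths. No direction of bias between arms is established.

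The live-birth case set for fresh stillbirths and the composite is an error of definition. It moves the risk ratio by at most about 2.6%, for assumed control risks up to 50 per 1,000 and true ratios between 0.5 and 1, and random error is far larger.

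S1 is secondary, and P1 to P3 and the sample size are untouched. The point should be corrected because the plan is wrong as written and the correction is cheap.

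**What to change.** 1. **Neonatal outcome.** Add to Tool 5 a separate count of neonatal deaths under 24 hours, with a one-sentence rule for abstractors, and use that count for both the neonatal and the composite rows of Table 5. Register pages are photographed in both arms and abstracted at the office (Section III.A), so the field can be filled from the images if the register records age or time of death. The documents do not say whether it does. If it does not, rename the outcome in S1 and in both Table 5 rows to what is actually counted.
2. **Denominator.** For the fresh stillbirth and composite rows, replace the live-birth case set with one that includes the stillbirths, and name it as the Poisson offset. Live births plus fresh stillbirths is the set at risk of intrapartum death; total births, which adds macerated stillbirths, is an acceptable alternative if stated in advance. Live births remain right for the neonatal row.

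The cost is one abstraction field, or a change of name, and an edit to three rows of Table 5. Tool 5 already collects the counts needed for either denominator.
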